SAMPLE SIZE DETERMINATION	Assuming an effect size of 0.32 [REDACTED] on the change in WOMAC pain score from Baseline to Week 4 between active HP-5000 [REDACTED] and HP-5000 [REDACTED] treatments and placebo, the probability for detecting the clinically meaningful effect size [REDACTED] or higher will be approximately 67% having 75 evaluable subjects per each active arm and 150 evaluable subjects in the placebo arm. Having 3 treatment arms, the total number of subjects randomized in the study and included in the primary analysis set should be

	approximately 300. A sufficient number of subjects will be screened to randomize the proposed sample size.
STUDY TREATMENT DURATION	The maximum treatment duration for each subject is 4 weeks. The total duration of study participation for each subject is approximately 9 weeks.

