3.1. Overall Design

3.2. Sample Size and Power

Assuming an effect size of [REDACTED] on the change in WOMAC pain score from Baseline to Week 4 between active (HP-5000 [REDACTED] and HP-5000 [REDACTED] treatments and placebo, the probability for detecting the clinically meaningful effect size [REDACTED] or higher will be approximately 67% having 75 evaluable subjects per each active arm and 150 evaluable subjects in the placebo arm. Having 3 treatment arms, the total number of subjects randomized in the study and included in the primary analysis set should be approximately 300. A sufficient number of subjects will be screened to randomize the proposed sample size.

In case of lower subject enrollment, the power to detect clinically meaningful effect of active treatments may drop but not below the threshold of 40%.

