4.1. Introduction

Data processing, tabulation of descriptive statistics, calculation of inferential statistics, and graphical representations will be performed using SAS® (release 9.4 or higher). If the use of other software is warranted, the final statistical methodology report will detail what software was used for what purposes.

Continuous variable summaries will include the number of subjects or patches (n) with non-missing values, mean, standard deviation (SD), median, minimum, and maximum. Where appropriate, estimates will be presented with 95% confidence intervals (CIs) and standard error (SE).

Categorical variable summaries will include the frequency and percentage of subjects or patches that are in the particular category or each possible value. In general the denominator for the percentage calculation will be based upon the study population for the specified treatment group and overall, unless otherwise specified. The denominator for by-visit displays will be the number of subjects (or patches) in the relevant study population with non-missing data at each visit.

The minimum and maximum will be reported with the same degree of precision (i.e., the same number of decimal places) as the observed data. Measures of location (mean and median) will be reported to 1 degree of precision more than the observed data and measures of spread (SD, SE) will be reported to 2 degrees of precision more than the observed data. Plasma concentration data will be treated as three significant figures for reporting purposes. Percentages will be presented to 1 decimal place, unless otherwise specified.

Unless otherwise indicated, all statistical tests will be conducted at the 0.05 significance level using 2-tailed tests, and p-values will be reported in pvalue6.4 format. Corresponding 95% CIs will be presented for statistical tests.

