4.2. Interim Analysis and Data Monitoring

No interim analysis is currently planned. If an interim analysis is planned in the future, this will be amended in protocol and in the SAP text as applicable.

5. Analysis Populations

The following 4 analysis populations are planned for this study:

- **Intent-to-Treat (ITT):** Includes all consented and randomized subjects. Regardless of any protocol deviations, analyses performed on the ITT set will be based on the randomized treatment assignment and all available data.
- **Full Analysis Set (FAS):** Includes all randomized subjects who have had at least 1 patch of double-blind study drug applied and who have a Baseline WOMAC pain score and at least 1 post-Baseline assessment of the primary efficacy measure (WOMAC pain score). Evaluable subjects will be defined as those who meet the FAS definition. The FAS will be used as the primary set for analysis of efficacy endpoints based on treatment actually received.
- **Safety Analysis Set (SAF):** Includes all subjects who have had at least 1 patch of double-blind study drug applied and who have at least 1 post-dose safety measurement during the double-blind treatment phase. In the unlikely event that errors may have occurred in treatment arm assignments, then analyses using the SAF will be based on treatment actually received. The SAF will be used for the analysis of dermal evaluations and safety endpoints.
- **Pharmacokinetic Analysis Set (PAS):** Includes all subjects who have received at least 1 patch of double-blind active study drug applied and who have at least 1 blood sample for PK assessment. Subjects may be excluded from the PAS set if they significantly violate inclusion or exclusion criteria, significantly violate the protocol in a way that may influence the PK analysis, if any unexpected error occurs during the study that may influence the PK analysis (e.g., early detachment of transdermal systems, apparent sample switching, etc.) or if their data are unavailable or incomplete. Excluded cases will be documented together with the reason for exclusion. In the unlikely event that errors may have occurred in treatment arm assignments, then analyses using the PAS will be based on treatment actually received.

Inclusion in the analysis populations described above will be determined prior to database lock.

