7.1. Primary Efficacy Analysis

The estimand in the primary analysis for efficacy for each dose is the difference between treatments groups (each HP-5000 treatment group vs. placebo) in the change from Baseline to Week 4 in WOMAC pain score in all subjects as randomized, under the assumption that all randomized patients remain on their randomized treatment throughout the trial.

AD-ST-33.04 Effective date: 30-Jun-2017

Version 1.0 | Date 21-Oct-2019 | AD-PR-109.01 Effective date: 26-Jun-2017

Page 24 of 124

Statistical Analysis Plan,
 Sponsor Noven Pharmaceuticals, Inc.
 Protocol Number HP-5000-US-05
 [REDACTED]

The comparisons of interest are:

- HP-5000 [REDACTED] versus placebo
- HP-5000 [REDACTED] versus placebo

WOMAC scores obtained 24 hours after removal/detachment of the study medication or WOMAC scores obtained within 24 the subject used rescue medication will be excluded as outliers. Outliers will be defined *a priori* as (i) WOMAC scores obtained more than 24 hours after removal/detachment of double-blind study medication; or (ii) WOMAC scores obtained within 24 hours the subject used rescue medication.

The change from Baseline to Week 4 in the WOMAC pain score will be analyzed using a mixed model repeated measures (MMRM) analysis. The MMRM model will include change from baseline in WOMAC pain score as the repeated dependent variable, with treatment (HP-5000-[REDACTED], HP-5000-[REDACTED], and placebo), visit, treatment-by-visit interaction, and the baseline WOMAC pain score as covariates. The mean difference of change will be compared for each active treatment arm, and overall active against placebo. An unstructured covariance matrix will be assumed. If the unstructured matrix fails to converge, a series of other covariance structures will be tested (AR(1), Toeplitz, and Compound Symmetry). The covariance structure which converges with the lowest Akaike information criterion (AIC) score will be chosen and noted in the resulting table. The Kenward-Roger approximation for denominator degrees of freedom will be implemented, and the restricted maximum likelihood (REML) approach for estimation will be specified in the model code.

Below is example SAS code for conducting the MMRM analysis specified. Note, the macro wrapper used in different covariance structures is not shown below (specified with type option):

[figure not shown]
[figure not shown]
[figure not shown]
```
ods output lsmeans = lsmn1
      lsmestimates = lsmest1

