In addition, sensitivity analyses will be performed to test the robustness of the primary result. As described in detail in Section [7.1.1](#), multiple imputation and pattern-mixture models will be implemented on the WOMAC pain score data using the FAS. These analyses are useful in determining if missing-at-random (MAR) and not-missing-at-random (NMAR) missingness patterns are impactful to the model effects and results. These analyses will be performed according to the National Academy of Sciences (2010) guidelines^{[10](#)}.

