14.2 Efficacy Tables		
14.2.1.1	FAS	Summary of WOMAC Pain Score by Study Visit
14.2.1.2.1	FAS	MMRM Analysis of WOMAC Pain Score at Week 4
14.2.1.2.2	FAS	MMRM Analysis of WOMAC Pain Score by Study Visit
14.2.1.2.3	ITT	MMRM Analysis of WOMAC Pain Score by Study Visit
14.2.1.4	FAS	ANCOVA Analysis on Rank-Transformed WOMAC Pain Score by Study Visit
14.2.1.5.1	FAS	MMRM Analysis of WOMAC Pain Score, Multiple Imputation by Study Visit, Discontinuation as Intercurrent Event
14.2.1.5.2	FAS	MMRM Analysis Of WOMAC Pain Score, Multiple Imputation By Study Visit, Rescue Medication As Intercurrent Event
14.2.1.6.1	FAS	MMRM Analysis of WOMAC Pain Score, Pattern-Mixture Model by Study Visit, Discontinuation as Intercurrent Event
14.2.1.6.2	FAS	MMRM Analysis of WOMAC Pain Score, Pattern-Mixture Model by Study

AD-ST-33.04 Effective date: 30-Jun-2017

Version 1.0 | Date 21-Oct-2019 | AD-PR-109.01 Effective date: 26-Jun-2017

Page 39 of 124

Statistical Analysis Plan,
 Sponsor Noven Pharmaceuticals, Inc.
 Protocol Number HP-5000-US-05
 [REDACTED]

		Visit, Rescue Medication as Intercurrent Event
14.2.1.7	FAS	Responder Analysis of WOMAC Pain Score by Study Visit
14.2.2.1	FAS	Summary of WOMAC Stiffness Score by Study Visit
14.2.2.2	FAS	MMRM Analysis of WOMAC Stiffness Score by Study Visit
14.2.2.3	FAS	Responder Analysis of WOMAC Stiffness Score by Study Visit
14.2.3.1	FAS	Summary of WOMAC Physical Function Score by Study Visit
14.2.3.2	FAS	MMRM Analysis of WOMAC Physical Function Score by Study Visit
14.2.3.3	FAS	Responder Analysis of WOMAC Physical Function Score by Study Visit
14.2.4.1	FAS	Summary of WOMAC Composite Score by Study Visit
14.2.4.2	FAS	MMRM Analysis of WOMAC Composite Score by Study Visit
14.2.4.3	FAS	Responder Analysis of WOMAC Composite Score by Study Visit
14.2.5.1	FAS	Summary of Patient Global Assessment by Study Visit
14.2.5.2	FAS	MMRM Analysis of Patient Global Assessment by Study Visit
14.2.5.3	FAS	Responder Analysis of Patient Global Assessment by Study Visit
14.2.6.1	FAS	Summary of Patient Global Impression of Change by Study Visit
14.2.6.2	FAS	MMRM Analysis of Patient Global Impression of Change by Study Visit
14.2.6.3	FAS	Responder Analysis of Patient Global Impression of Change by Study Visit
		Summary of Pain Intensity Assessed on an 11-Point Numeric Rating Scale (NRS) by Study Visit
14.2.7.1	FAS	MMRM Analysis of Pain Intensity Assessed on an 11-Point Numeric Rating Scale (NRS) by Study Visit

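### Randomized subjects with no post-baseline WOMAC pain score enter no planned analysis of the primary endpoint, because all the imputation analyses are restricted to the FAS

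*SAP*

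**What the plan says.** SAP section 7.1 defines the target of the primary analysis as the difference in change from Baseline to Week 4 "in all subjects as randomized, under the assumption that all randomized patients remain on their randomized treatment throughout the trial". SAP section 5 admits a subject to the FAS only with a patch applied, a baseline score and "at least 1 post-Baseline assessment of the primary efficacy measure (WOMAC pain score").

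The same section 7.1 says that "multiple imputation and pattern-mixture models will be implemented on the WOMAC pain score data using the FAS". The table list in SAP 13.1 agrees: tables 14.2.1.5.1, 14.2.1.5.2, 14.2.1.6.1 and 14.2.1.6.2 are all labelled FAS.

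One table uses the ITT set: 14.2.1.2.3, titled "MMRM Analysis of WOMAC Pain Score by Study Visit". Its shell describes the primary mixed model with change from baseline as the dependent variable. SAP 5.1.4 says that missing values are not imputed in the main efficacy analyses.

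Protocol 10.1.2 places randomization on Day 0 and the first patch at home the next day. The schedule of events puts the first scheduled post-baseline WOMAC at Day 7, plus or minus 2 days. Protocol 10.1.5 makes the Early Termination Visit mandatory after Baseline and includes the WOMAC in it.

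**The concern.** The estimand covers everyone randomized, but the FAS is defined partly by something that happens after randomization and could differ by arm. The rationale for Method 2 in SAP 7.1.1 is that a subject who stops is on no active drug and should not be credited with benefit. That applies most directly to someone who leaves in the first days, yet a subject with only a baseline score is never passed to Method 2.

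The ITT table may appear to close the gap because its population label includes these subjects, but its model cannot use them. Agreement between the ITT and FAS tables would therefore say nothing about them.

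**Working it through.** **1. Which planned analyses could count a subject with a baseline score only?**

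| Analysis of WOMAC pain | Set | Counts such a subject? |
|---|---|---|
| Primary mixed model | FAS | No, not in the set |
| Rank ANCOVA, responder analysis, subgroups | FAS | No, not in the set |
| Multiple imputation, two tables | FAS | No, not in the set |
| Pattern-mixture, two tables | FAS | No, not in the set |
| Table 14.2.1.2.3 | ITT | In the set, but no record in the model |

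The programming notes for the four imputation tables say to repeat the shell of 14.2.1.2.3, which is an ITT shell. The titles of those tables say Full Analysis Set, as does section 7.1, so the note is best read as governing layout only.

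**2. Does the ITT model use them?** One trial of 75, 75 and 150 subjects was simulated with three post-baseline visits. It was analysed by REML with unstructured covariance, treatment-by-visit means and baseline. Eighteen subjects (six per arm) had no post-baseline score.

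| Fit | Subjects supplied | Records used | Week 4 differences (SE) |
|---|---|---|---|
| FAS | 282 | 790 | −0.932614 (0.482995); −1.583760 (0.478524) |
| ITT | 300 | 790 | −0.932614 (0.482995); −1.583760 (0.478524) |

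The 18 extra subjects change nothing. When two placebo-randomized subjects were moved to the first active arm, to mimic a FAS grouped by treatment received, the differences became −0.808 and −1.551. The two fits can therefore part for other reasons.

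**3. Effect of including them under Method 2.** Let the placebo mean change be m, the treatment effect δ, and p the share of an active arm with only a baseline score. Imputed placebo-like, the arm mean is

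(1 − p)(m + δ) + p·m = m + (1 − p)δ,

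so the difference from placebo is (1 − p)δ. The proportional loss is p, whatever δ is.

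**4. Orientation on the SAP's sample size.** Section 3.2 states that the power "will be approximately 67% having 75 evaluable subjects per each active arm and 150 evaluable subjects in the placebo arm". Section 4.1 says that "all statistical tests will be conducted at the 0.05 significance level using 2-tailed tests". The effect size is redacted in the SAP and the current protocol. A superseded protocol version in the same file reads "Assuming an effect size of 0.32", with the remainder redacted.

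- SE = √(1/75 + 1/150) = 0.141 in standardized units.
- Power at 0.32: Φ(0.32/0.1414 − 1.96) = Φ(0.303) = 61.9%.
- An effect of about 0.34 gives 67.2%.

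The stated 67% is therefore not reproduced from 0.32. With the operative value redacted, that does not show it to be wrong, and nothing here depends on it. Taking 0.32 as an assumed effect, and p as an assumption applied to every arm with variance unchanged:

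| p | Subjects per active arm (75p) | Effect if imputed placebo-like | Power | Power if left out (n reduced, effect 0.32) |
|---|---|---|---|---|
| 2% | 1.5 | 0.314 | 60% | 61% |
| 5% | 3.75 | 0.304 | 58% | 60% |
| 10% | 7.5 | 0.288 | 53% | 57% |
| 15% | 11.25 | 0.272 | 49% | 55% |

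At 5% the shift is 0.32 × 0.05 = 0.016, about 0.11 of a standard error (0.016/0.141).

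**The case against.** The strongest reply is that the Early Termination Visit already captures most of these people. Someone who stops on Day 3 for skin irritation and attends that visit has a post-baseline WOMAC, is in the FAS, and so falls within both imputation methods. This stands and sets the size of the point. A reader might infer that all first-week withdrawals vanish from the analysis; Protocol 10.1.5 does not support that. One uncertainty remains. Section 7.1 excludes scores taken more than 24 hours after patch removal or within 24 hours of rescue use, and the SAP does not say whether an excluded score still counts for FAS entry. If it does not, the group is larger.

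A reader might also infer that the ITT and FAS tables must agree exactly. They need not. The SAP groups the FAS by treatment received and the ITT by randomized arm, and a subject who never applied a patch but has a post-baseline score is in the ITT only. Neither route brings in a subject without a post-baseline score.

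Third, the estimand is hypothetical and the model assumes missing at random. Under that assumption, given baseline, leaving out baseline-only subjects does not bias the mixed-model difference. This also stands and is why the FAS model can stay primary. It does not help the sensitivity analyses, whose purpose is to relax that assumption.

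Finally, Table 14.1.1 already shows FAS counts by arm and Listing 16.2.1.1 gives each subject's reason for exclusion. The exclusions would be visible, but their effect on the estimate would not.

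**Conclusion.** The point holds for a narrow group: subjects randomized but with no post-baseline WOMAC pain score, meaning those who leave before Week 1 and also miss the Early Termination Visit. No planned analysis of the primary endpoint imputes or otherwise counts them, and for them the ITT mixed model adds nothing to the FAS model.

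The size depends on p, which the documents do not give. Section 3.2 makes no allowance for such losses: "the total number of subjects randomized in the study and included in the primary analysis set should be approximately 300". Under placebo-based imputation the effect falls by the proportion p, which is modest at any plausible rate and small against the standard error at 5%. This is a gap in the robustness checks that should be closed. The documents do not support reading it as a fault in the primary analysis.

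**What to change.** In SAP 7.1 and the table list in 13.1, change the population for tables 14.2.1.5.1, 14.2.1.5.2, 14.2.1.6.1 and 14.2.1.6.2 from the FAS to all ITT subjects with a baseline WOMAC pain score, grouped by randomized arm. The planned methods can take this. Method 1 starts at the baseline visit and imputes forward from baseline covariates, and the monotone step of Method 2 regresses the score on baseline. A subject with only a baseline score is then imputed from baseline.

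Keep the FAS mixed model as primary. Keep table 14.2.1.2.3, which is the only efficacy table grouped as randomized, and footnote that it does not address subjects without a post-baseline score. State in section 5 whether a score excluded under the 24-hour rules counts for FAS entry.

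The cost is new population labels for four sensitivity tables, a footnote and a rerun of code already planned. No new data are needed. The imputed effect may come out slightly smaller.

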7.1.1. Primary Efficacy Analysis Sensitivity Analyses

Analysis of sensitivity to missing data for the primary endpoint will be performed as follows. For the primary efficacy endpoint of WOMAC pain, the following two imputation methods will be implemented to assess the impact of missing data and robustness of the primary analysis.

Method 1: Multiple Imputation (MI), after subject uses rescue medication (intercurrent event)

MI assumes that the statistical behavior of drug- and placebo-treated patients after discontinuing study medication becomes that of the study cohort. Multiple-imputations are used to replace missing outcomes for patients who have prematurely withdrawn from the study using multiple draws from the posterior predictive distribution estimated from the treatment arms.

Data are processed sequentially by repeatedly calling SAS® PROC MI to impute missing outcomes at visit $t = 1, \dots, T$. The following procedure is followed:

- *Initialization (Step 1)*. Set $t = 0$ (baseline visit).
- *Iteration (Step 2)*. Set $t = t + 1$. Create a dataset combined records from drug- and placebo-treated patients with columns for covariates \mathbf{X} and outcomes at visits $1, \dots, t$ with outcomes for all patients set to missing at visit t and set to observed or imputed values at visits $1, \dots, t-1$.
- *Imputation (Step 3)*. Run Bayesian regression in SAS® PROC MI on this data to impute missing values for visit t using previous outcomes for visit 1 to $t-1$ and baseline covariates.
 - Replace imputed data for all patients at visit t with their observed values, whenever available. If $t < T$ then go to Step 2, otherwise proceed to Step 4.
 - Repeat steps 1-3, m times with different seed values to create m imputed complete datasets. In this analysis, m will be assigned 1000.
- *Analysis (Step 4)*. For each completed dataset use the model as it would have been applied had the data been complete for the continuous outcome. The final inference on treatment difference is conducted from the multiple datasets using Rubin's combining rules, as implemented in SAS® PROC MI ANALYZE.

Method 2: Placebo-based Pattern-mixture model (PMM)

PMM is similar to MI but differs in that the strategy for missingness. Possible imputations do not come from the whole study cohort as mentioned above, but on the placebo group for the whole population. The idea is that discontinued subjects would be taking zero dose of the study drug after discontinuation and thus no longer exhibit any benefit from the treatment. In the above specified Step 3, instead of pulling from the entire study cohort, we will only draw from the placebo arm. The steps for this approach are detailed below:

1. Impute all non-monotone (intermittent) missing data using the MCMC method of PROC MI. Note that this imputation will sample data within each treatment group. SAS pseudo code is provided below.

```
PROC MI DATA=example seed = 6654 NIMPUTE = 20 OUT = outdata1;
  BY <treatment>;
  MCMC chain=multiple impute=monotone;
  VAR <treatment> <baseline> <V1> <V2> <V4>;
RUN;
```

AD-ST-33.04 Effective date: 30-Jun-2017

2. Using the imputed datasets from Step #1 that are now monotone missing (no intermittent missing data), a single call to PROC MI (including the MNAR statement) will be utilized to impute the monotone missing data.

SAS pseudo code is provided below. SAS accomplishes this iterative process in one step. Note that the treatment level 3 is the placebo treatment group:

```
PROC MI DATA=example seed = 2617 NIMPUTE = 20 OUT = outdata1;
  BY <time>;
  CLASS <treatment>;
  MONOTONE REG (<score> = <baseline> / details);
  MNAR MODEL (<score> / modelobs=(<treatment>=3));
  VAR <treatment> <baseline> <score>;
RUN;
```

3. When all missing data are imputed, PROC MIANALYZE will be used to combine the parameters from the analyses for inference.

Method 1 and 2 are MAR-based MI and pMI respectively. After MI, MMRM (same as primary analysis model) will be applied to imputed dataset.

Thus, there are two intercurrent events (discontinuation and use of rescue medication) and two imputation strategies (MAR-based MI and pMI). The following table provides more details how they will be used.

Summary of Analyses after intercurrent events				
Analysis	Method	Discontinuation	Rescue Med.	Comment
Primary	MMRM	NO	YES	
Sensitivity (1)	MMRM	pMI	YES	Method 2
Sensitivity (2)	MMRM	MAR-based MI	MAR-based MI	Method 1, Rescue Med. as a intercurrent event

Rules for handling missing or partial AE, concomitant medication data are described in Section [5.1.7](#).

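### SAP 7.1.1 mis-specifies both sensitivity analyses: Method 1 leaves no outcome to fit and carries a MAR label its text does not support, and Method 2's code drops the earlier visits its text uses

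*SAP*

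**What the plan says.** **Method 1.** Step 2 of SAP 7.1.1 creates a dataset of all patients "with outcomes for all patients set to missing at visit" t, with observed or imputed values kept at earlier visits. Step 3 runs "PROC MI on this data to impute missing values for visit" t, using earlier outcomes and baseline covariates. Observed values are put back only after that. The covariate set X is not listed and no treatment term is named. On the source of the draws, the section says "MI assumes that the statistical behavior of drug- and placebo-treated patients after discontinuing study medication becomes that of the study cohort", and also "multiple draws from the posterior predictive distribution estimated from the treatment arms".

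**Method 2.** The text contrasts itself with Method 1: "Possible imputations do not come from the whole study cohort as mentioned above, but on the placebo group for the whole population". It then changes one thing in Method 1's Step 3: "instead of pulling from the entire study cohort, we will only draw from the placebo arm". The code for monotone (dropout) missingness runs separately `BY <time>` with "MONOTONE REG (<score> = <baseline> / details" as the regression. Its VAR list holds treatment, baseline and one score. The code for intermittent missingness, by contrast, lists all three visits.

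**Label.** "Method 1 and 2 are MAR-based MI and pMI respectively". SAP 5.1.4 explains MAR as implying that dropouts behave like completers in their own arm.

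**Tables.** SAP 13.1 lists four imputation tables: MI and pattern-mixture, each for discontinuation and for rescue. The shells send each back to 7.1.1. The summary table there defines two runs: placebo-based MI for discontinuation, and MAR-based MI for both events.

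**The concern.** A sensitivity analysis tells the reader something only if its assumption is known and its code delivers it. Here Method 1 cannot be estimated, and the possible repairs (own arm, treatment as covariate, pooled arms) are different analyses. Method 2's code may well run, but it fits a different model from the one described, so the mismatch could pass unnoticed. SAP 4 places the final analyses after lock and unblinding. If the choice is still open then, someone will make it with the results in reach. If Method 1 is repaired by pooling, it also stops being a MAR check and nearly duplicates the placebo-based analysis.

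**Working it through.** The plan gives no figure on this point to reproduce. Steps 1 to 3 are textual and settle the finding; steps 4 to 6 only size it.

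**1. Method 1: responses available to the fit.** After Step 2 the number of observed visit-t outcomes is 0, at each of Weeks 1, 2 and 4. A regression with no observed response cannot be estimated. Restoring observed values afterwards does not help, because the fit has already been asked for.

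**2. Method 1: label against source.** Three statements in 7.1.1 give the cohort as the source (one under Method 1, two under Method 2). One refers to the treatment arms without saying within arm. The label says MAR, which 5.1.4 ties to each patient's own arm. The likelier reading is pooled arms, which is not MAR when treatment has an effect. If treatment belongs to the unlisted X, the label is right and the cohort wording is wrong.

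**3. Method 2: text against code.**

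| | Predictors of visit t | Fitted on |
|---|---|---|
| Text (Step 3 by reference) | baseline and all earlier visits | placebo |
| Code | baseline only, one visit at a time | placebo |

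The code excludes earlier visits twice: through the regression effect and through the BY line.

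**4. Hand calculation, Method 2.** Assumptions: Week 4 effect 0.32 SD (synopsis of a superseded protocol version in the same file; the current figure is redacted); change-score SD 1; between-visit correlation ρ; correlation with baseline -0.4; random dropout at rate p in both arms, half after Week 1 and half after Week 2; effects d1 and d2 at Weeks 1 and 2.

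- Code: active dropouts are given no benefit, so the estimate is (1 - p) × 0.32.
- Text: dropouts carry forward a benefit c, so the estimate is (1 - p) × 0.32 + p × c, and the gap is p × c.
- Partial correlation given baseline: r = (ρ - 0.16)/(1 - 0.16).
- Leaving after Week 1: c1 = r × d1. Leaving after Week 2: c2 = [r/(1 + r)] × (d1 + d2). c is their mean.

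With ρ = 0.65, d1 = 0.16, d2 = 0.24: r = 0.49/0.84 = 0.583; c1 = 0.093; c2 = 0.368 × 0.40 = 0.147; c = 0.120.

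| p | Code | Text | Gap |
|---|---|---|---|
| 10% | 0.288 | 0.300 | 0.012 |
| 20% | 0.256 | 0.280 | 0.024 |
| 30% | 0.224 | 0.260 | 0.036 |

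At the extremes, ρ = 0.5 with the same effects gives c = 0.090, and ρ = 0.8 with 0.32 at every visit gives c = 0.260. At 30% dropout the gap therefore runs from 0.027 to 0.078.

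**5. Large-sample simulation.** 100,000/100,000/200,000 subjects; ρ 0.5, 0.65 or 0.8; effect 0.32 throughout or 0.16/0.24/0.32; dropout random or logistic in the last score (slope 1 per SD); five rate pairs; 60 scenarios. Rescue use was not modelled.

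- Treatment in the imputation model: 0.316 to 0.324 throughout.
- Equal 10/20/30%: pooled Method 1 averages 0.305/0.291/0.274 and lies within 0.008 of the Method 2 text. The Method 2 code is 0.008-0.026, 0.018-0.055 and 0.027-0.081 below its text, in line with step 4.
- 10% active, 30% placebo: code 0.007-0.027 below text if dropout is random, 0.065-0.130 below if score-dependent.
- 30% active, 10% placebo: code 0.026-0.077 below text if random; from 0.007 below to 0.039 above if score-dependent.
- If half of the dropouts have no usable Week 1 or 2 score, the code-text gap roughly halves (0.003-0.041 with equal dropout).

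A separate run of the central case (ρ = 0.65, rising effect, score-dependent dropout) gave:

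| Active/placebo dropout | With treatment | Pooled | Method 2 text | Method 2 code |
|---|---|---|---|---|
| 20/20% | 0.318 | 0.278 | 0.277 | 0.256 |
| 30/30% | 0.321 | 0.260 | 0.257 | 0.224 |
| 10/30% | 0.321 | 0.278 | 0.299 | 0.207 |
| 30/10% | 0.320 | 0.277 | 0.259 | 0.289 |

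**6. Trial size (75/75/150, 600 trials per rate pair, 20 imputations, score-dependent dropout).** Method 2 text and code disagree on p < 0.05 in 8, 15 and 18% of trials at equal 10, 20 and 30%, in 26% at 10/30 and in 12% at 30/10. For scale, a similar run (500 trials per setting) showed that repeating the text version with a new seed already changes the call in 3 to 5%.

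**7. Tables.** Table 14.2.1.6.1 matches the first defined run and 14.2.1.5.2 the second. For 14.2.1.5.1 and 14.2.1.6.2 the handling of the other intercurrent event is not stated.

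**The case against.** The primary MMRM is unaffected. None of the six top-line tables in SAP 13.1 is an imputation table, and protocol 13.4.3.1 only allows for such analyses. Method 1's blanking fails visibly and its intent can be guessed. X is unspecified and may include treatment, in which case the MAR label is correct. The Method 2 text gives as its rationale that dropouts lose all drug benefit, and for active dropouts the baseline-only code fits that better than the text model, which carries part of the on-treatment benefit forward. Every dropout rate here is assumed, and the largest gaps come from one lopsided scenario.

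Much of this stands as a limit on severity. The MAR point is the likelier reading, not a proof, and the raw disagreement rates include seed noise. It does not remove the error. Guessing the intent of Method 1 does not choose between own-arm and pooled repair. The Method 2 text applies Step 3, and its monotone step, described as iterative, makes sense only across visits. The code also discards placebo dropouts' own scores. In one check (assumed effect 0.34 SD, correlation 0.6, about 20% dropout driven by the Week 2 score) their mean Week 4 pain was 0.41 in truth, 0.40 under the text and 0.19 under the code.

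**Conclusion.** The point holds: 7.1.1 is wrong as written and should be fixed before unblinding. Method 1 cannot be estimated, and its label and its described source do not agree. Method 2's text and code are different models. The two undefined tables, taken alone, are missing detail.

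Under an assumed 0.32 SD effect, the size is modest at equal 10% dropout (code 0.008 to 0.026 SD below text). It becomes large enough to change a reading of robustness when dropout depends on pain and differs by arm, and there the direction depends on which arm loses more. Rates and mechanism are assumptions, since the documents give none. The primary MMRM, and its contrast with a placebo-based analysis, survive.

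**What to change.** - **Method 1:** keep observed visit-t outcomes when fitting and impute only the missing ones. List X. Include treatment or impute by arm; if pooling is intended, say so and drop the MAR label.
- **Method 2, dropout step:** take the Step 1 output in wide format, `BY _Imputation_` with `NIMPUTE=1`; regress each visit on baseline and all earlier visits; give an MNAR model with placebo as `MODELOBS` for each visit. Remove treatment from the Step 1 VAR list, where it is already the BY variable.
- **Tables 14.2.1.5.1 and 14.2.1.6.2:** state how the other intercurrent event is handled, for example with two more rows in the 7.1.1 summary table.

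The cost is SAP text and a few lines of SAS, with no new data. With treatment in the model, Method 1 largely repeats the MMRM assumption for discontinuation, and what it adds is the handling of rescue use. The SAP should say so.
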